9. Be able to swallow and retain oral medication and must not have any clinically significant gastrointestinal abnormalities that may alter absorption.
10. Have adequate organ function as defined in [Table 1](#):

Table 1 Inclusion Criteria Laboratory Parameters

System	Laboratory Value
Hematological	
ANC	$\geq 1,500/\text{mcL}$
Platelets	$\geq 100,000/\text{mcL}$
Hemoglobin	$\geq 9 \text{ g/dL}$ or $\geq 5.6 \text{ mmol/L}$
Renal	
Serum creatinine OR Measured or calculated ^a CrCl (GFR can also be used in place of creatinine or CrCl)	$\leq 1.5 \times \text{ULN}$ OR $\geq 60 \text{ mL/min}$ for subject with creatinine levels $>1.5 \times$ institutional ULN
Hepatic	
Serum total bilirubin	$\leq 1.5 \times \text{ULN}$ OR Direct bilirubin $\leq \text{ULN}$ for subjects with total bilirubin levels $>1.5 \times \text{ULN}$
AST (SGOT) and ALT (SGPT)	$\leq 2.5 \times \text{ULN}$ OR $\leq 5 \times \text{ULN}$ for subjects with liver metastases
Coagulation	
INR or PT aPTT	$\leq 1.5 \times \text{ULN}$ unless the subject is receiving anticoagulant therapy as long as PT or aPTT is within therapeutic range of intended use of anticoagulants

^a Calculate CrCl using standard Cockcroft-Gault formula (Appendix 12.3).
 ALT (SGOT)=alanine aminotransferase; ANC=absolute neutrophil count; aPTT=activated partial thromboplastin time; AST (SGPT)=aspartate aminotransferase; CrCl=creatinine clearance; GFR=glomerular filtration rate; INR=International Normalized Ratio; PT=prothrombin time; ULN=upper limit of normal.

11. Female subject of childbearing potential must have a negative urine or serum pregnancy test within 72 hours prior to receiving the first dose of study medication. If the urine test is positive or cannot be confirmed as negative, a serum pregnancy test will be required. The serum pregnancy test must be negative for the subject to be eligible.

12. Female subjects may be enrolled in the trial if they are:

- Of nonchildbearing potential, which is defined as:
 - A female subject ≥ 45 years of age and has not had menses for greater than 1 year,
 - A female who is amenorrheic for >2 years without a hysterectomy and oophorectomy and a follicle-stimulating hormone (FSH) value in the postmenopausal range upon pretrial (screening) evaluation,
and/or

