Part 2: MK-8353 will be administered at the RP2D(s) identified for MK-8353 in Part 1 of the study (several doses and schedules could be explored), in combination with pembrolizumab at a fixed dose of 200 mg (same fixed dose as in Part 1). The decision to bring specific schedule(s) or dose(s) into the expansion cohorts in Part 2 will be based on exposure parameters, as well as the safety profile and potential preliminary efficacy observed, and will be made jointly by the investigators and the Sponsor.

Throughout the study (Part 1 and Part 2) in Arms A and B, the first dose of MK-8353 will occur at the trial site on Day 1 of each cycle, shortly before the pembrolizumab infusion. Pembrolizumab will be then administered through an IV infusion as described in the Pharmacy Manual. For optional Arm C, administration will follow the schedule described in **Table 2**. For optional Arm D, after the screening visit, the subject will receive MK-8353 monotherapy unsupervised at his/her home from Cycle 1, Day 1 to Day 14, prior to Cycle 2 Day 1.

1. Arm A (bid continuous):
 - For the cohorts in Arm A (bid schedule), subsequent dosing of MK-8353 will be performed in the evening of the same day (Day 1), and then twice a day by the subject (ie, unsupervised at his/her home) at approximately the same time each day, until Day 1 of the next cycle.
2. Arm B (qd continuous):
 - In Arm B (qd schedule), subsequent dosing of MK-8353 will be performed the next day (Day 2), and then once a day by the subject (ie, unsupervised at his/her home) at approximately the same time each day, until Day 1 of the next cycle.

3. Optional Arm C (1 week on/1 week off):

- In optional Arm C (1 week on/1 week off qd schedule), subsequent dosing of MK-8353 will be performed the next day by the subject (ie, unsupervised at his/her home) at approximately the same time each day, on Days 1 to 7, Days 15 to 21, and Days 29 to 35 of a 42-day period (corresponding to 2 cycles of 21 days) until Day 1 of Cycle 3.

4. Optional Arm D (monotherapy run-in then continuous):

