4. Record medications taken 4 weeks prior to C1D1 and all medications taken up to and including 30 days after the last dose of study drug or the End of Treatment (whichever is later). Refer to inclusion/exclusion criteria for prohibited medications and washout periods.
5. Must be performed within 3 days prior to Day 1 of each cycle. Physical examination, ECOG Performance Status, ECG, vital signs, and screening laboratory tests must be performed within 3 days prior to C1D1. It is not necessary to repeat C1D1 testing if the Screening testing was performed within 7 days prior to C1D1. Full physical examination will be performed at the Screening Visit and at the Treatment Discontinuation Visit. Directed physical examination will be done as indicated at all other visits.
6. Perform standard 12 lead ECG reporting ventricular rate, PR and QRS duration, and QT/QTcF intervals prior to any blood collections or other study procedures.
7. Vital signs include blood pressure, pulse rate, and respiratory rate while sitting; temperature, height (at screening only), and weight.
8. After Cycle 1, MK 8353 may be dispensed up to 3 days prior to the cycle start to coincide with the physical exam. In Arm A, MK 8353 will be administered continuously, twice a day. In Arm B, MK 8353 will be administered continuously, once a day. In optional Arm C, MK 8353 will be administered 1 week on/1 week off, orally, qd, on Days 1 to 7, Days 15 to 21, and Days 29 to 35 of a 42 day period (corresponding to 2 cycles of 21 days) until Day 1 of Cycle 3, when this 42 day period will start again. Study drug may only be dispensed after the treating physician has confirmed the subject will continue on to the next cycle. Each cycle is 21 days. Subjects may receive treatment for up to 35 cycles.
9. Pembrolizumab will be administered via IV infusion on Day 1 of each cycle (except for Cycle 1 [MK 8353 monotherapy run in] of optional Arm D). Refer to Figure 2 for dosing instructions. Each cycle is 21 days (except for Cycle 1 [MK 8353 monotherapy run in] of optional Arm D). Subjects may receive treatment for up to 35 cycles.

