	Up to 28 days Prior to Cycle 1 Day 1	Days 1 to 14	Day 1	Day 8	Day 15	Day 1 ¹	Day 15	Day 1		At Treatment Discontinuation	30 days after the last dose	90 days after the last dose	Approximately every 12 weeks post discontinuation
Scheduling Window (Days) ¹	28 to 15		±3	±3	±3	±3 ¹	±3	±3	±7		±7	±7	±7
Prothrombin Time (PT)/International Normalized Ratio (INR) and Activated Partial Thromboplastin Time (aPTT) ¹⁹	X												
Tumor Markers (CEA, CA 125, and CA 19-9, as appropriate)	X		X			X		X		X	X		
Serum or Urine Pregnancy Test if applicable ²⁰	X		X										
HIV/Hepatitis Screen ²¹	X												
Thyroid Function (T3 or FT3, T4 or FT4, and TSH) ²²	X		X			X		X			X		
Anti pembrolizumab Antibodies (Part 1 only) ²³			X			X		X			X		
Optional On treatment Tumor Biopsy ^{2,24}							X						
Pharmacokinetics Evaluations													
Blood for MK 8353 PK assay ²⁵			X	X	X	X		X					
Blood for Pembrolizumab PK assay (Part 1 only) ²⁶			X			X		X			X		

1. Visits should occur within the prespecified days window (eg, +/- 3 days), except Cycle 3 Day 1, which should occur with a window of +3 days.
2. Screening procedures to be performed within 28 days prior C1D1, unless otherwise noted. Informed consent may be obtained more than 28 days prior to C1D1 to allow for tumor tissue collection.
3. Subject Identification Card must be given to subject at the start of study and must be collected when the subject is no longer participating in any portion of the study.
4. Record medications taken 4 weeks prior to C1D1 and all medications taken up to and including 30 days after the last dose of study drug or the End of Treatment (whichever is later). Refer to inclusion/exclusion criteria for prohibited medications and washout periods.
5. Must be performed within 3 days prior to Day 1 of each cycle. Physical examination, ECOG Performance Status, ECG, vital signs must be performed within 3 days prior to C1D1. It is not necessary to repeat C1D1 testing if the Screening testing was performed within 7 days prior to C1D1. Full physical examination will be performed at the Screening Visit and at the Treatment Discontinuation Visit. Directed physical examination will be done as indicated at all other visits.
6. Perform standard 12 lead ECG reporting ventricular rate, PR and QRS duration, and QT/QTcF intervals prior to any blood collections or other study procedures.

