15. Whole blood samples should be collected predose at Cycle 2, Cycle 3, Cycle 5, and again at discontinuation. Leftover specimens will be stored for FBR if the subject consents to FBR.
16. Hematology tests include complete blood count with 5 part differential and platelets.

17. Urine dipstick or microscopic urinalysis may be performed according to site SOP. Urine dipstick includes pH, protein, glucose, leukocyte, esterase, ketones, and nitrite. Mandatory microscopic urinalysis will be performed if the dipstick results are abnormal. Microscopic analysis includes white blood cell count, red blood cell count, epithelial cells and casts.
18. Serum Chemistry tests include sodium, potassium, calcium, phosphate, chloride, bicarbonate/CO₂ (if performed in region), BUN, creatinine (cystatin C could be evaluated if creatinine is abnormal), SGOT (AST), SGPT (ALT), total proteins, total bilirubin (direct bilirubin if abnormal), albumin, alkaline phosphatase, glucose, uric acid, amylase, lipase, lactate dehydrogenase (LDH), and γ glutamyltransferase (GGT). . Cystatin C may be conducted by central vendor only if analysis was not available from local study site laboratory.
19. Coagulation factors (PT/INR and aPTT) should be tested as part of the screening procedures for all subjects. Furthermore, any subject receiving anticoagulant therapy should have coagulation factors monitored closely throughout the trial.
20. For women of reproductive potential, a urine pregnancy test will be performed at Screening and within 72 hours prior to the first dose of study treatment. If a urine pregnancy test cannot be confirmed as negative, a serum pregnancy test is required and must be negative. Monthly pregnancy testing should be conducted as per local regulations where applicable.
21. HIV testing should include HIV Type 1 and Type 2 (eg, HIV 1/2 antibody screening test and evaluation of HIV viral load as needed). Hepatitis testing should include HCV, RNA (qualitative), or Hepatitis C antibody, and HBsAg.
22. Samples for thyroid function testing should be collected on Day 1 of Cycle 2 and on Day 1 of Cycle 3. Following Cycle 3, testing will be performed every other cycle (ie, Cycles 2, 3, 5, 7, etc., +/- 3 day window) and at the Posttreatment Safety Follow up Visit. Analysis of T3 or FT3, T4 or FT4, and TSH will be performed by the local study site laboratory (conducted by central vendor only if analysis was not available from local study site laboratory).

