7.1.5.1 Screening Period

During the screening period, potential subjects will be evaluated to determine whether or not they fulfill the entry requirements as detailed in Section 5.1.

Written informed consent must be obtained prior to performing any protocol-specific procedures. Results of tests performed prior to the subject signing consent as part of routine clinical management are acceptable in lieu of a screening test if performed within the specified time frame.

Screening procedures, including tumor imaging, are to be completed within 28 days prior to the first dose of study treatment except for screening laboratory tests which are to be performed within 3 days prior to the first dose of study treatment.

Screening procedures may be repeated after consultation with the Sponsor.

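### The optional Arm D flow chart contradicts its own footnotes and the eligibility text on when pregnancy and safety laboratory tests precede the first MK-8353 dose

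*Combined protocol and SAP*

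**What the plan says.** **First dose.** Section 5.2 says that in Arm D, after screening, "the subject will receive MK-8353 monotherapy unsupervised at his/her home from Cycle 1, Day 1 to Day 14". The first dose of study medication is therefore on Cycle 1 Day 1 of the run-in. Pembrolizumab starts at Cycle 2 Day 1.

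**Arm D grid (Section 6).**
- The Screening column is headed "Up to 28 days Prior to Cycle 1 Day 1", and its scheduling window is 28 to 15.
- The row "Serum or Urine Pregnancy Test if applicable" is marked at Screening and Cycle 2 Day 1. Hematology and chemistry are marked at Screening and then from Cycle 2 Day 1 onward.
- In the Cycle 1 run-in column, only dispensing of MK-8353 is marked, apart from the survival-status arrow.

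**Notes on those same rows.** Note 20 says "a urine pregnancy test will be performed at Screening and within 72 hours prior to the first dose of study treatment". Note 5, attached to hematology and chemistry, opens "Must be performed within 3 days prior to Day 1 of each cycle".

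**Text for all arms.** Under inclusion criterion 11, a woman of childbearing potential "must have a negative urine or serum pregnancy test within 72 hours prior to receiving the first dose of study medication". Section 7.1.5.1 allows 28 days for screening, "except for screening laboratory tests which are to be performed within 3 days prior to the first dose of study treatment". Neither makes an exception for Arm D. Section 7.1.5.2 starts the Arm D study visits at Cycle 2.

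**Arms A to C chart.** The Screening window is 28 to 1, and these tests are marked at Screening and Cycle 1 Day 1. Note 5 there names screening laboratory tests among the procedures due within 3 days of Cycle 1 Day 1; the matching Arm D sentence leaves them out. Both versions of note 5 then add "It is not necessary to repeat C1D1 testing if the Screening testing was performed within 7 days prior to C1D1". Notes 16 and 18 for Arms A to C give 3 days for hematology and chemistry. The Arm D versions give no number of days.

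**The concern.** Sites tend to book visits and tests from the grid. A site that followed the Arm D marks and the printed window would test at least 15 days before the first dose. It would next test after the 14-day home run-in. That would depart from inclusion criterion 11 for women of childbearing potential, and from Section 7.1.5.1 for every Arm D subject.

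The pregnancy criterion and the organ-function limits in Table 1 are meant to describe the subject when dosing starts. Section 7.1.3.1 also asks for acceptable laboratory results before each MK-8353 dose. A change arising between the two marked tests might not be seen until two weeks of MK-8353 had been taken.

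**Working it through.** No sample-size or power figure is involved. The check counts days and compares the passages.

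**Inputs.** Set Cycle 1 Day 1 (first MK-8353 dose) as day 0. The run-in lasts 14 days, so Cycle 2 Day 1 is day +14, with a visit window of ±3 days. The Screening cell is taken as days before its anchor. The required windows are the 3 days (72 hours) before day 0. The note 5 waiver uses 7 days.

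| Reading of the Screening cell | Screening days relative to first dose | Overlap with the 3-day window | Overlap with the 7-day waiver | Days from Screening to Cycle 2 Day 1 |
|---|---|---|---|---|
| Arm D, 28 to 15 from Cycle 1 Day 1 (as headed) | −28 to −15 | none | none | 15 + 14 = 29 to 28 + 14 = 42 |
| Arm D, 28 to 15 from Cycle 2 Day 1 | 14 − 28 = −14 to 14 − 15 = −1 | −3 to −1 | −7 to −1 | 15 to 28 |
| Arms A to C, 28 to 1 from Cycle 1 Day 1 | −28 to −1 | −3 to −1 | −7 to −1 | not needed |

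With the ±3-day visit window, the first row becomes 29 − 3 = 26 to 42 + 3 = 45 days.

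The Cycle 2 Day 1 mark follows 14 days of dosing under either Arm D reading. Only the Screening mark could meet a requirement tied to the first dose, and as headed it cannot.

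**Note 5 for laboratory tests, side by side.**
- Arms A to C: 3 days in one sentence, 7 days in the waiver that follows; 3 days in notes 16, 18 and Section 7.1.5.1. A subject tested on days −7 to −4 gets conflicting instructions.
- Arm D: the general opening sentence gives 3 days before every cycle, but the sentence on Cycle 1 Day 1 does not name laboratory tests. Section 7.1.5.1 gives 3 days.

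**The case against.** The strongest answer is that the footnotes belong to the chart. Notes 5 and 20 sit on the very rows at issue, and inclusion criterion 11 and Section 7.1.5.1 say the same. This stands. A reader might infer that Arm D subjects would start MK-8353 with no current pregnancy or laboratory test. The documents do not support that, because they require those tests before the first dose.

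The notes still do not settle where the tests happen. The grid gives them no column, and Section 7.1.5.2 starts Arm D visits at Cycle 2. Section 7.1.4.3 brings subjects in on Day 1 of each 21-day cycle, whereas Cycle 1 of Arm D lasts 14 days. Dispensing is marked in the run-in column, and note 8 makes dispensing depend on the physician's confirmation, so some contact with the site is likely. Nothing ties the tests to it.

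A second answer is that 28 to 15 may have been counted from Cycle 2 Day 1. Screening could then meet the windows, and the 15-day floor rests on that one cell. This is plausible, but the documents do not say so, and the column heading would then be wrong.

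A reader might also infer that the baseline for laboratory dose-limiting toxicities is out of date. The laboratory criteria in Section 5.2.1.5 rest on grade, intervention, hospitalization and persistence. They do not refer to a baseline value, so that inference fails.

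For Arms A to C, the specific notes 16 and 18 can be read as overriding the general waiver in note 5. That makes the conflict there minor, though it remains in the wording.

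**Conclusion.** The Arm D grid and its visit text contradict the chart's own footnotes, inclusion criterion 11 and Section 7.1.5.1. Read as printed, no marked pregnancy, hematology or chemistry test falls in the required pre-dose window. The last marked test is 15 to 28 days before the first dose, and the marked tests are nominally 29 to 42 days apart. This rests on taking the Screening heading literally. If the cell was counted from Cycle 2 Day 1, the error lies in the heading.

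This is an inconsistency in an operational schedule, and the protocol as a whole does not omit the tests. It should be corrected before Arm D opens, in Part 1 or Part 2, because sites act on the grid. The pregnancy element concerns only women of childbearing potential. The note 5 wording in Arms A to C is a smaller conflict that applies whether or not Arm D opens.

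**What to change.** 1. Reconcile the anchor and range of the Arm D Screening cell with its heading, notes 2, 5 and 20, inclusion criterion 11 and Section 7.1.5.1.
2. Show in the Arm D grid and in Section 7.1.5.2 where the tests already required before the first dose take place.
3. Reconcile note 5 in each chart with Section 7.1.5.1 and, for Arms A to C, with notes 16 and 18. State in Arm D note 5 whether its Cycle 1 Day 1 sentence covers screening laboratory tests.

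The sponsor should settle the day counts; the need is that every passage gives the same ones. The cost is flow-chart, footnote and visit wording in an amendment. No new procedure is added, because the text already calls for these tests. The small downside is that Arm D subjects may need them drawn when MK-8353 is dispensed.

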7 TRIAL PROCEDURES

7.1 Trial Procedures

The Trial Flow Chart - Section 6.0 summarizes the trial procedures to be performed at each visit. Individual trial procedures are described in detail below. It may be necessary to perform these procedures at unscheduled time points if deemed clinically necessary by the investigator.

Furthermore, additional evaluations/testing may be deemed necessary by the investigator and or the Sponsor for reasons related to subject safety. In some cases, such evaluation/testing may be potentially sensitive in nature (eg, HIV, Hepatitis C, etc.), and thus local regulations may require that additional informed consent be obtained from the subject. In these cases, such evaluations/testing will be performed in accordance with those regulations.

7.1.1 Administrative Procedures

7.1.1.1 Informed Consent

The investigator or qualified designee must obtain documented consent from each potential subject or each subject's legally acceptable representative prior to participating in a clinical trial or Future Biomedical Research. If there are changes to the subject's status during the trial (eg, health or age of majority requirements), the investigator or qualified designee must ensure the appropriate consent is in place.

7.1.1.1.1 General Informed Consent

Consent must be documented by the subject's dated signature or by the subject's legally acceptable representative's dated signature on a consent form along with the dated signature of the person conducting the consent discussion.

A copy of the signed and dated consent form should be given to the subject before participation in the trial.

The initial informed consent form, any subsequent revised written informed consent form and any written information provided to the subject must receive the IRB/ERC's approval/favorable opinion in advance of use. The subject or his/her legally acceptable representative should be informed in a timely manner if new information becomes available that may be relevant to the subject's willingness to continue participation in the trial. The communication of this information will be provided and documented via a revised consent form or addendum to the original consent form that captures the subject's dated signature or by the subject's legally acceptable representative's dated signature.

Specifics about a trial and the trial population will be added to the consent form template at the protocol level.

The informed consent will adhere to IRB/ERC requirements, applicable laws and regulations and Sponsor requirements.

7.1.1.1.2 Consent and Collection of Specimens for Future Biomedical Research

The investigator or qualified designee will explain the Future Biomedical Research consent to the subject, answer all of his/her questions, and obtain written informed consent before performing any procedure related to Future Biomedical Research. A copy of the informed consent will be given to the subject.

7.1.1.2 Inclusion/Exclusion Criteria

All inclusion and exclusion criteria will be reviewed by the investigator or qualified designee to ensure that the subject qualifies for the trial as per Sections 5.1.2 and 5.1.3.

7.1.1.3 Subject Identification Card

All subjects will be given a Subject Identification Card identifying them as participants in a research trial. The card will contain trial site contact information (including direct telephone numbers) to be utilized in the event of an emergency. The investigator or qualified designee will provide the subject with a Subject Identification Card immediately after the subject provides written informed consent. At the time of treatment allocation/randomization, site personnel will add the treatment/randomization number to the Subject Identification Card.

The subject identification card also contains contact information for the emergency unblinding call center so that a health care provider can obtain information about trial medication/vaccination in emergency situations where the investigator is not available.

